1.6. Randomization and Masking

Subjects will be randomly assigned to either J JVCI Investigational Contact Lens (Test) or ACUVUE® OASYS® (Control) groups based on a computer-generated randomization schedule prepared before the study by the study biostatistician. The randomization will be stratified by study site and randomly permuted blocks of 2 assignments will be used to achieve 1:1 test versus control lens type ratio within each study site. The assignment of subjects will be performed at the first visit prior to the first fitting. The following must have occurred prior to assignment:

- Informed consent has been obtained
- It has been determined that the subject meets all the inclusion / exclusion criteria
- Subject history and baseline information has been collected

When the trial fitting assessment is ready to be conducted, the following steps should be followed:

1. Investigator or designee (documented on the Delegation Log) will consult the randomization scheme to obtain the study test article assignment for that subject prior to dispensing.
2. Investigator or designee will record the subject's number on the appropriate line of the randomization scheme.

3. Investigator or designee will pull the appropriate test articles from the study supply. All test articles that were opened, whether dispensed or not, must be recorded on the Test Article Accountability Log in the “Lenses Dispensed” section.

This will be a partially-masked study. The identity of the study lenses will be masked to the subject and as much as possible to the investigator.

The following procedures will be followed:

- Subjects will not be aware of the identity of the study contact lenses.
- Investigators involved in the data collection will be masked as to the identity of the study lenses.

This is a partially-masked study. The dynamic nature (variable shade) of the Test lens makes full masking impossible. However, the identity of the Control lenses will be masked to the subject by way of investigational foil. This will reduce the likelihood that habitual wearers of ACUVUE OASYS recognize the Control lens and increase the likelihood that questionnaires will be answered unbiasedly.

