4.4.2 OPTIONAL FLOWCHART

4.5 RANDOMIZATION AND MASKING

Subjects will be randomly assigned to either JJVCI Investigational Contact Lens (Test) or ACUVUE OASYS (Control) groups based on a computer-generated randomization schedule prepared before the study by the sponsor Biostatistician. The randomization will be stratified by study site and randomly permuted blocks of 4 assignments will be used to achieve 1:1 Test versus Control lens type ratio within each study site.

The study site must follow the randomization scheme provided and complete enrollment according to the randomization list and not pre-select or assign subjects. The randomized assignment of subjects will be performed at the first visit prior to the first fitting. The following must have occurred prior to randomization:

- Informed consent has been obtained
- Subject meets all the inclusion / exclusion criteria
- Subject history and baseline information has been collected

This is a partially subject masked study. The dynamic nature (variable shade) of the Test lens makes full masking impossible. However, the identity of the Control lenses will be masked to the subject by way of investigational foil. This will reduce the likelihood that habitual wearers of ACUVUE OASYS recognize the Control lens and increase the likelihood that questionnaires will be answered unbiasedly.

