4.10 PROCEDURES FOR MAINTAINING AND BREAKING RANDOMIZATION CODES

Each type of test article except for the subject's habitual spectacles is assigned and labeled with a unique lens ID code (also serves as the randomization code). The identity of the control lens type (Oasys) will be masked to subjects.

The test article mask shall not be broken unless information concerning the lens type is necessary for the urgent medical treatment of a subject. The Sponsor should be notified before the mask is broken.

When dispensing test articles, the following steps should be followed to maintain randomization codes:

1. The designee (documented on the delegation log) will consult the randomization scheme to obtain the study test article assignment for that subject prior to dispensing.

2. The designee will record the subject's number on the appropriate line of the randomization scheme.

The designee will pull the appropriate test articles from the study supply. All test articles that were opened, whether dispensed or not, must be recorded on the Test Article Accountability Log in the "Dispensed" section.

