1. INTRODUCTION

1.1. Background

This document describes the data analysis specifications for protocol CR-5638 titled “Long-term Evaluation of [REDACTED] UV Blocker”. The test article is the J JVCI Investigational Contact Lens [REDACTED] while the control is ACUVUE® OASYS®. This study is 2- Phase randomized, 8-visit, partially subject-masked (Control arm only), 14-week dispensing trial. The study lenses will be worn as daily wear (DW) for a period of 12 weeks, with follow-up visits occurring after 1-, 2-, 4-, 8- and 12-weeks. All visits up to visit 6 are considered to be Phase I of the study while visits 7 and 8 are considered to be Phase II of the study. After the 12-week follow-up has occurred (Phase I has completed); the habitual lenses will be worn for a period of two weeks with weekly visits (Phase II).

The document is intended to describe the guidance for statistical analysis up to the 12-week follow up (Phase 1) and will supersede section 9 in the protocol if there are any discrepancies (i.e. See Amendment History section)

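### SAP 1.6 (blocks of 2) and Protocol 4.5 (blocks of 4) conflict on block size; either fixed size lets site staff who know it be certain of a third to a half of assignments

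*SAP*

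**What the plan says.** SAP 1.6 and Protocol 4.5 each describe a single computer-made list, drawn up in advance by the biostatistician, with 1:1 allocation at each site. They differ on block size.

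- SAP 1.6, with site as the stratum: "randomly permuted blocks of 2 assignments will be used".
- Protocol 4.5, with the same stratum: "randomly permuted blocks of 4 assignments will be used to achieve 1:1 Test versus Control lens type ratio".

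SAP 1.1 says the SAP "will supersede section 9 in the protocol if there are any discrepancies". Randomization is in protocol section 4, outside that clause. The SAP amendment history lists only the original version and explains no change of block size.

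On handling at the site, SAP 1.6 and Protocol 4.10 have a site designee (in the SAP, the investigator or a designee) look up the scheme, write the subject's "number on the appropriate line of the randomization scheme" and take the lenses from stock. Protocol 4.10 gives each type of article a "unique lens ID code (also serves as the randomization code".

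On masking, both documents accept that the Test lens's changing shade rules out full masking. Special foil hides the Control lens's identity from the subject. SAP 1.6 also says that investigators who collect data will be masked, but gives no means of achieving this.

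Both documents require consent, confirmed eligibility, and history and baseline data before assignment. Protocol 4.5 also tells sites not to choose subjects for particular assignments. Neither document describes envelopes, central release, varying block sizes or keeping the block size from sites. An interactive voice response system appears only in the SAP's abbreviation list.

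**The concern.** One list cannot have two block sizes, so at least one document misdescribes the randomization.

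The second issue is concealment. Within a fixed block, once one arm's places are used up, the rest of the block is determined. Someone who knows the block size and the earlier assignments at the site then knows the next lens before deciding whom to screen, when to book them, or how to judge a discretionary criterion such as whether a subject seems willing to comply.

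If enrolment were steered this way, the arms could differ at baseline. Eyestrain caused by glare, a co-primary efficacy endpoint, is subject-reported. Its model in SAP 5.2.2 contains lens group, time, iris category, their interactions and site. It does not include the baseline glare score, although Protocol 4.7.1 collects one at Visit 1 before lens assignment. A baseline difference in that score would therefore carry into the Test minus Control comparison unadjusted.

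**Working it through.** No sample size, power or alpha in the documents depends on block size, so there is no stated figure to reproduce. The check enumerates the possible blocks.

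**Inputs.** Block size 2 (SAP 1.6) or 4 (Protocol 4.5), 1:1 within site. 120 subjects, 6 sites, 15 to 25 per site (Protocol 4.4). Assumptions: 120 / 6 = 20 subjects at each site, and staff know the block size and all earlier assignments at their own site.

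**Measures.** An assignment is certain when only one arm has places left in the block. The best guess is the arm with more places left, or a coin toss if they are equal.

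**Blocks of 2** (TC, CT). The first position is never certain and the second always is.
- Certain: (0 + 1) / 2 = 50%, or 60 of 120.
- Guessed correctly: (1/2 + 1) / 2 = 75%, or 90 of 120.

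**Blocks of 4** (TTCC, TCTC, TCCT, CTTC, CTCT, CCTT, equally likely). Position 3 is certain only when the first two match, in 2 of 6 sequences. Position 4 is always certain.

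| Position | Certain | Guessed correctly |
|---|---|---|
| 1 | 0 | 1/2 |
| 2 | 0 | 2/3 |
| 3 | 1/3 | 1/3 × 1 + 2/3 × 1/2 = 2/3 |
| 4 | 1 | 1 |

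- Certain: (1/3 + 1) / 4 = 1/3, or 40 of 120.
- Guessed correctly: (1/2 + 2/3 + 2/3 + 1) / 4 = 17/24 = 71%, or 85 of 120.

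With no information, 60 of 120 would be guessed correctly.

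**By site size.** For sites of 15, 20 and 25 subjects, the number certain is 7, 10 and 12 with blocks of 2. With blocks of 4 it averages 4.3, 6.7 and 8.0.

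**Can earlier assignments be known?** The person who pulls the lenses sees the type code given to each earlier subject, and the shade of the Test lens is a second route. The SAP's statement that investigators are masked does not close either route for staff who handle the scheme and stock.

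**A varying scheme, for comparison.** With blocks of 4 and 6 in random order at equal chance, over the first 14 subjects at a site, and a guesser who knows the two possible sizes but not their order, about 6% of assignments are certain and 68% are guessed correctly.

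**The case against.** The strongest reply is that the mismatch is a drafting error, cured by stating the size actually used, and that predictability is a separate matter needing facts the documents do not supply. Several parts of this stand.

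- A reader might infer that sites can foresee every second assignment. That requires both that the list uses blocks of 2 and that staff know it. The 2 appears only in the SAP, and nothing shows that sites receive the SAP. On the protocol's text the figure is 33%.
- A reader might infer that every assignment is known because sites hold the list. The documents neither state nor exclude that later lines can be read ahead.
- A reader might call the primary endpoint an open-label questionnaire. The design is partially masked, and logMAR acuity is co-primary alongside eyestrain. Bias from subjects recognizing the Test lens is a different problem, which no block scheme removes.
- Safeguards exist. Eligibility and baseline data come before assignment, and several entry gates are measured: over-refraction, best-corrected acuity and slit-lamp grade. These narrow the discretion through which foreknowledge could act.
- The trial is exploratory by its own description.

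The reply does not dispose of the point. Measured gates and an instruction not to pre-select restrain behaviour but do not hide the next assignment while staff decide whom to screen and when. Exploratory status does not excuse two incompatible descriptions of one list.

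**Conclusion.** The contradiction is literal and unresolved. The predictability holds as a conditional range: if staff know past assignments and the true block size, 33% (protocol) to 50% (SAP) of assignments are certain and 71% to 75% can be guessed. The counts of about 40 and 60 of 120 assume 20 subjects at each of 6 sites.

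The documents show an opportunity for selection bias. They do not show that it was used, and they do not allow its effect on any endpoint to be sized. They also do not show which block size is correct. Who can read ahead on the list is an open question for the sponsor. The change is advisable and does not bear on the sample size.

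**What to change.** State one scheme in SAP 1.6 and Protocol 4.5, and align Protocol 4.10 with it:

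- Use randomly varying block sizes within site, for example 4 and 6, held only by the sponsor biostatistician and removed from text that sites receive.
- Release each assignment singly after eligibility is confirmed, in place of a list that could be read ahead. Sequential opaque envelopes would do. So would the EDC if it supports this, but Protocol 10.1 and Appendix C describe it only for data capture and lens accountability.
- Say who at the site may see the scheme, and reconcile the SAP's statement on investigator masking with the acknowledged visibility of the Test lens.

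The two main changes do different work. Varying sizes cut certainty from 33–50% to about 6% but lower the best-guess rate only to about 68%. Single release closes any route to reading ahead.

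The cost is a regenerated list, some rewording and the set-up of the release method. Within-site imbalance could reach 3, against 1 with blocks of 2 or 2 with blocks of 4.

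If the list is already in use, correct both texts to the scheme actually applied, report who could see the list, and compare baseline variables, including the glare score, by arm within site.

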2. GENERAL ANALYSIS DEFINITIONS

2.1. Pooling Algorithm for Analysis Centers

Data will be pooled from multiple study centers for this analysis. The justification for pooling comes from three critical factors: the study sites follow one common protocol, the sponsor provides close monitoring of study site compliance, and the study sites use common data collection procedures.

2.2. Analysis Sets

2.2.1. Efficacy Analysis Set

Efficacy analyses will be performed on all randomized subjects who completed the study and did not substantially deviate from the protocol as determined by the trial cohort review committee prior to database hard lock (Per-protocol population). Justification of excluding subjects with protocol deviations in the analysis population will be documented in a memo to file. Additional post-hoc analyses may be conducted by including all randomized subjects who have been successfully dispensed and have at least one follow-up visit (i.e. all available data).

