4.2 INCLUSION CRITERIA

Potential subjects must satisfy all of the following criteria to be enrolled in the study:

Subjects should meet all study Inclusion Criteria as outlined below:

1. The subject must read and sign the Informed Consent form.
2. The subject must appear able and willing to adhere to the instructions set forth in this clinical protocol.
3. Healthy adult males or females age ≥ 18 years of age with signed informed consent. Eligible presbyopes will be those that wear full distance contact lenses in both eyes, then wear reading glasses over them.
4. The subject's optimal vertexed spherical equivalent distance correction must be between -1.00 and -6.00D.
5. The subject's refractive cylinder must be ≤ 1.00 D in each eye.
6. The subject must have visual acuity best correctable to 20/25+3 or better for each eye.
7. Subjects should own a wearable pair of spectacles.
8. The subject is a current spherical soft contact lens wearer (defined as a minimum of 6 hours of DW per day, at least 5 days per week, for a minimum of 1 month prior to the study) and willing to wear the study lenses on a similar basis.
9. Subjects must be able and willing to wear the study lenses at least 6 hours a day, a minimum of 5 days per week
10. The subject must have normal eyes (i.e., no ocular medications or infections of any type).

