5	Lens Fit Assessment:	
The fit of the lens is judged by the investigator as pass or fail based on the criteria below. If the fit of the lens is judged as a failure, the subject is terminated from the study. To be judged as a failure, the lens must display one or more of the following:
 
 1. Limbal exposure in any gaze 2. Edge lift 3. Insufficient and/or excessive movement in all three movement categories 	
6	Lens Deposits	Record the front and back surface deposits of the lenses.	
7	Lens Wettability	Record the white light lens wettability of both lenses.	
8	Continuance	
For the subject to continue in the study, they must meet all three of the following criteria:
 
 1. Visual acuity is 0.17 logMAR (20/30) or better OD and OS 2. The lens fit is acceptable OD and OS 3. Investigator approval. If the investigator does not approve the dispensing of the first study lens, then the study is terminated for that subject. 	

VISIT 1: DISPENSING #1		Day 0
The following information will be collected:		
Steps	Details	
1	
Dispense
 
The lenses will be dispensed for 6-8 days.
 
 1. The subjects should wear their lenses similar to the inclusion criteria: ≥ 6 hours per day, ≥ 5 days per week. 2. The lenses will be worn as daily wear only. 3. All subjects will be provided Opti-Free PureMoist to be used in a rub regime. 4. Preservative-free rewetting drops are permitted if needed. 5. A patient instruction booklet will be provided. 6. The lenses must be stored in the supplied case out of direct sunlight. 
Note 1: In the event a lens is lost or damaged, the subject will return to the investigator site for replacement (extra lenses cannot be given at the dispensing visit).
 
Note 2: The subject's habitual contact lenses cannot be worn until during Visit 6 when they are placed back into their habitual lenses.
	
2	
Follow-up Visit Scheduling
 
An appointment for the next visit should be made for approximately 7 days (range 6-8 days) after Visit 1. Subjects should be advised to wear the study lenses at least 6 hours a day, and a minimum of 5 days per week. The study lenses must be worn into the Follow-up Visit.
	

VISIT 2: 7-DAY FOLLOW-UP		(Follow-up #1, 6-8 days after Visit 1)
The following information will be collected:		
Steps	Details	

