18	Lens Removal & Storage	
The worn lenses will be removed, stored in the following manner, and returned to the Sponsor:
 
 1. OD and OS lens stored wet in a labeled vial with Opti-Free PureMoist. The lenses should not be rubbed. 2. The lenses will be stored and shipped cold (refrigerated or frozen). 	
19	Slit Lamp Findings	
Slit Lamp Classification Scale [REDACTED] will be used to grade the findings. Record only whole numbers.
 
Note: Subject must be free of any FDA grade 3 or greater slit lamp findings with no active ocular infection/inflammation.
	
20	Eye Rinse	The study coordinator, investigator, or technician will rinse the subject's eyes thoroughly with saline.	

VISIT 3: LENS ASSIGNMENT #2		(6-8 days after Visit 2)
The following information will be collected:		
Steps	Details	
1	Lens Information	The same lens type and power of the previous study lens must be chosen. The investigator or subject will place the lenses on. Quickly check for any lens damage and replace if necessary.
2	Lens Damage	Lens damage (draw in source document and describe). Replace lens if damaged and complete the [REDACTED] form and save lens in vial with saline.

VISIT 3: FITTING #2		(6-8 days after Visit 2)
The following information will be collected:		
Steps	Details	
1	Time Interval	Please wait at least 5 minutes before continuing.
2	Spherical Over-refraction	Perform a spherical over-refraction OD and OS using any acceptable means (i.e., phoropter, trial lenses, flipper bars) in normal room illumination and record the resultant distance Snellen visual acuity OD and OS. A 0.00 D spherical over-refraction must be achieved to continue.
3	Lens Modification Criteria	The lens power will be modified if the over-refraction is ± 0.25 D or more in either eye. One modification attempt is allowed.

VISIT 3: TRIAL FITTING LENS MODIFICATION		(If needed, one modification is allowed)
The following information will be collected:		
Steps	Details	
1	Lens Information	The lens power will be chosen based on the over-refraction results from the first trial lenses.
2	Lens Damage	Lens damage (draw in source document and describe). Replace lens if damaged and complete the [REDACTED] form and save lens in vial with saline.
3	Time Interval	Please wait at least 5 minutes before continuing.

VISIT 3: TRIAL FITTING LENS MODIFICATION		(If needed, one modification is allowed)	
The following information will be collected:			
Steps	Details		

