4	Spherical Over-refraction	Perform a spherical over-refraction OD and OS using any acceptable means (i.e., phoropter, trial lenses, flipper bars) in normal room illumination and record the resultant distance Snellen visual acuity OD and OS. If a 0.00 D spherical over-refraction OD and OS is not demonstrated, the subject is terminated from the study; complete the Final Evaluation.	

VISIT 3: FITTING #2, CONTINUED		(6-8 days after Visit 2)
The following information will be collected:		
Steps	Details	
1	Subject-reported Ocular Symptoms	The subject will respond to a Symptoms Questionnaire.
2	Dispensing Questionnaire	Subjects will respond to the Dispensing Questionnaire for initial comfort and vision (ID: ISOC0001, ISOV0001)
3	LogMAR (ETDRS) Visual Acuity	Using the Sekonic light meter with ISO1 setting of 125 under high illumination (>7.3 EV) and high chart luminance (9.9-10.7 EV) record the distance ETDRS high contrast: 1. OD: Chart HC1 2. OS: Chart HC2 3. OU: Chart HC3
4	Lens Fit Assessment:	The fit of the lens is judged by the investigator as pass or fail based on the criteria below. If the fit of the lens is judged as a failure, the subject is terminated from the study. To be judged as a failure, the lens must display one or more of the following: 1. Limbal exposure in any gaze 2. Edge lift 3. Insufficient and/or excessive movement in all three movement categories
5	Lens Deposits	Record the front and back surface deposits of the lenses.
6	Lens Wettability	Record the white light lens wettability of both lenses.

VISIT 3: FITTING #2, CONTINUED**(6-8 days after Visit 2)****The following information will be collected:**

Steps		Details	
7	Continuance	
For the subject to continue in the study, they must meet all three of the following criteria:
 
1. Visual acuity is 0.17 logMAR (20/30) or better OD and OS.2. The lens fit is acceptable OD and OS3. Investigator approval. If the investigator does not approve the dispensing of the first study lens, then the study is terminated for that subject.	

VISIT 3: DISPENSING #2**(6-8 days after Visit 2)****The following information will be collected:**

Steps		Details	

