9.1 STATISTICAL METHODS TO BE EMPLOYED

This section is a general outline of the statistical methods that will be implemented in this clinical trial. For more details, refer to the stand-alone Statistical Analysis Plan (SAP) of this clinical study.

General Considerations:

Statistical programming and analyses will be performed using SAS (SAS Institute, Cary, NC) Version 9.4 or higher. Throughout the analysis of data, the results for each eye will be used when available for summarization and statistical analysis.

Descriptive statistics will be reported at baseline and each post fit time period for all safety and efficacy variables as appropriate. Unless otherwise noted, continuous variables will be summarized using descriptive statistics: number of non-missing values (N), mean (Mean), standard deviation (SD), median (Median), minimum (Min), and maximum (Max); and categorical variables will be summarized using the frequency count (N) and the percentage (%) of subjects or eyes in each category.

Summaries will be presented by study article type (Test or Control) and will be performed separately by completion status (completed or discontinued). See Section 9.7 for additional details regarding subject completion status. The denominator for percentages of counts will be the same for each visit on the summary tables and will equal the final number of subjects or eyes in the group under consideration. Unscheduled visits will be summarized separately and will be excluded from efficacy analysis.

Analysis Population Sets:

Efficacy analyses will be performed on all randomized subjects who completed the study and did not substantially deviate from the protocol as determined by the trial cohort review committee prior to database hard lock (Per-Protocol Population). Justification of excluding subjects with protocol deviations in the per-protocol population set will be documented in a memo to file. Additional post-hoc analyses may be conducted by including all randomized subjects who have been successfully dispensed and have at least one follow-up visit. Refer to section 9.7 Evaluable Subjects for more details.

Safety analyses will be performed on the safety population, which will be comprised of all randomized subjects who have been successfully dispensed at least one study lens.

Unless otherwise specified, all statistical tests will be 2-sided and conducted at the 0.05 level of significance.

Efficacy Analysis:

Visual Acuity

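### The final efficacy models are limited to per-protocol completers, although the protocol stops subjects on lens acuity after randomization and already holds co-primary data from many of them

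*SAP*

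**What the plan says.** **Analysis set.** SAP 2.2.1 defines the efficacy set: "Efficacy analyses will be performed on all randomized subjects who completed the study and did not substantially deviate from the protocol". Protocol 9.1 has the same rule, so the two documents agree. The wider set is mentioned only as a possibility: "Additional post-hoc analyses may be conducted by including all randomized subjects who have been successfully dispensed and have at least one follow-up visit". SAP 4.2 counts a subject as a Phase I completer after every scheduled visit through Visit 6; Protocol 9.7 requires visits through Visit 8. A subject stopped at Visit 3, 4 or 5 is outside both definitions.

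**Stops after randomization.** Protocol 4.5 places randomization before the first fitting. In Protocol 4.7.1, one condition for continuing at Visits 1, 3, 4 and 5 is "Visual acuity is 0.17 logMAR (20/30) or better OD and OS". An unacceptable fit also ends participation, as does residual over-refraction after one power change: "If a 0.00 D spherical over-refraction OD and OS is not demonstrated, the subject is terminated from the study". At Visits 3, 4 and 5 these checks are made on a new pair: "The same lens type and power of the previous study lens must be chosen".

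**Data recorded before the check.** At Visits 3, 4 and 5 the glare questionnaire (step 6) and the worn-pair ETDRS acuity (step 13) come before the new pair is inserted.

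**Other provisions.** SAP 5.1.2 adds multiple imputation if dropout exceeds 15%, without naming an analysis set. The safety set in SAP 2.2.2 is all randomized, dispensed subjects. SAP 1.4 calls every hypothesis exploratory.

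**The concern.** Completion depends, after randomization, on a close correlate of one co-primary endpoint. If the Test lens gives worse acuity, more Test than Control subjects are stopped. Those who remain are the better-seeing ones, and the Test-Control difference shrinks. The acuity hypothesis is that the lenses do not differ, so shrinkage favours the conclusion the sponsor hopes for.

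Part of this loss is avoidable. The planned mixed models can use incomplete profiles, but the set definition removes those subjects before the model is fitted. At week 2 the loss after dispensing is wholly avoidable, because that reading is taken before the Visit 3 check. Leaving the wider analysis optional also means that the decision to run it could be taken after results are known.

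**Working it through.** **1. What a stopped subject has contributed.** Of the planned co-primary assessments (weeks 2, 4, 8 and 12):

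- Visit 3 stop: week 2 recorded, 1 of 4.
- Visit 4 stop: weeks 2 and 4, 2 of 4.
- Visit 5 stop: weeks 2, 4 and 8, 3 of 4.
- Visit 1 stop: none.

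**2. Historical losses (SAP 1.5).** Discontinued after dispensing: (4+2+6)/(88+69+106) = 12/263 = 4.6%. Enrolled but not dispensed: (1+2+3)/(89+71+109) = 6/269 = 2.2%. Both cover all reasons and come from shorter studies.

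**3. Size of the pull on acuity.** The plan gives no logMAR mean, SD or correlation, so everything here is illustrative.

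- Model: reading = arm mean + subject effect + eye effect + occasion error. A worn-pair and a new-pair reading of the same eye share the subject and eye effects only.
- Variance shares: 50/20/30% gives correlation 0.5+0.2 = 0.7; 35/15/50% gives 0.35+0.15 = 0.5.
- Control mean -0.10 to 0.00; SD 0.08 to 0.10.
- Entry screen on or off. The criterion is "The subject must have visual acuity best correctable to 20/25+3 or better for each eye", that is log10(1.25) - 3 × 0.02 = 0.037, taken as 0.04.
- Rule: both eyes 0.17 or better at Visit 1, and on the new pair at Visits 3, 4 and 5.
- 400,000 simulated subjects per arm. Scenarios are kept only if stops stay within the losses in step 2.

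Week-12 Test-Control difference for a true 0.05, correlation 0.7 (selected scenarios):

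| Control mean | SD | Entry screen | All dispensed | Completers | Same model, all available visits | Completer loss |
|---|---|---|---|---|---|---|
| -0.10 | 0.08 | no | 0.0493 | 0.0481 | 0.0491 | 0.0012 |
| -0.10 | 0.10 | no | 0.0473 | 0.0438 | 0.0467 | 0.0035 |
| -0.05 | 0.08 | no | 0.0470 | 0.0435 | 0.0464 | 0.0035 |
| -0.10 | 0.08 | yes | 0.0500 | 0.0496 | 0.0499 | 0.0004 |
| 0.00 | 0.10 | yes | 0.0479 | 0.0438 | 0.0469 | 0.0041 |

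Completer loss is the all-dispensed column minus the completers column. At correlation 0.5 it is 0.0007 to 0.0037. The standard error with 50 per arm is √(V_T/50 + V_C/50), where V is the variance of the two-eye mean among completers. It is 0.011 to 0.016, so the loss is 0.03 to 0.30 SE. At 0.02 logMAR per letter, 0.0041 is 0.2 of a letter.

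In the third row the week-2 figures are also 0.0470 and 0.0435, and stops after dispensing are 4.9% in Test against 1.1% in Control.

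- True difference 0.10 (correlation 0.7): loss 0.003 to 0.006, or 0.22 to 0.48 SE.
- True difference 0: 0.0001 or less.
- True 0.05, all available visits in the same model: 0.0001 to 0.0011 remains, at most 0.09 SE.
- Visit 1 selection takes a further 0 to 0.003 off the true 0.05. No follow-up-based set restores it.

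**4. Would the imputation analysis run?** 15% of 120 is 18, so the trigger needs 19 or more dropouts. The binomial probability is about 0.000002 at 4.6%, 0.03 at 10%, and 0.63 at the planned allowance of 10/60 = 16.7%.

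**The case against.** **The effect is small and its upper end is generous.** This stands. The largest figures treat nearly all of the historical loss as acuity failures (pooled stops up to 4.3% against 4.6%), and the documents give no count of acuity stops. Lens power is also brought to zero over-refraction before each acuity check, which removes spherical blur.

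**Stopped subjects are not ignored.** Also right. A reader might infer that no committed model uses their data. That is wrong: the safety GEE models run on all dispensed subjects. Protocol 9.1 also requires summaries by lens and completion status. The SAP "will supersede section 9 in the protocol if there are any discrepancies", and it does not conflict on this; SAP 6.4 itself tabulates acuity for discontinued eyes. The interim eyestrain analysis (SAP 3) is run at week 4, before Visit 6 completion can be known, and may include subjects who stop later. The gap is confined to the final efficacy models.

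**Imputation covers dropout.** Partly. One might infer that SAP 5.1.2 is empty because completers have no dropout to impute. The fairer reading is that it presupposes a set containing dropouts and fails to name it. If attrition reaches the planned 16.7%, it is more likely than not to run. At historical loss it almost certainly would not.

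**A wider set has its own dilution.** This stands: subjects with deviations may blur a real difference, and that dilution has not been quantified here. It is a reason to show both results, not to leave one optional.

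**Conclusion.** The point holds for the final models of acuity, eyestrain and wear time. They leave out collected co-primary data from subjects stopped at Visits 3, 4 or 5, and the analysis that would use those data is not committed.

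For acuity the result is a slight pull toward no difference if Test is truly worse: 0.0004 to 0.0041 logMAR of a true 0.05, and nil if there is no true difference. These figures rest on the assumed means, SDs and correlations, and on stops within historical losses. The reading of the text does not depend on them.

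Three stronger inferences are not supported:

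- *Selection on the endpoint itself.* The Visit 3, 4 and 5 checks use a new pair, so they select on a correlate of the worn-pair outcome. Only the Visit 1 check acts directly on acuity at dispensing.
- *Heavy shrinkage.* With Control mean 0.00 and SD 0.12, a true 0.05 can fall to 0.027 in completers. That figure includes Visit 1 selection (0.035 among all dispensed) and needs post-dispensing stops of 22% in Test and 14% in Control, far above 4.6%.
- *Biased eyestrain.* No rule removes subjects on eyestrain score. The established loss there is unused data.

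Because every hypothesis is exploratory, the consequence is modest. The change is still worth making, since it costs little and removes discretion over whether the wider analysis appears.

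**What to change.** - **SAP 2.2.1:** replace the optional post-hoc sentence with a commitment. Fit the same mixed model to all randomized subjects dispensed a study lens with at least one follow-up visit, analysed as randomized, using every available visit. Preferably make this the main efficacy estimate; in any case always report it beside the per-protocol result.
- **SAP 5.1.2:** name this wider set as the one on which multiple imputation is run.
- **Disposition (SAP 4.2):** report Visit 1 fitting stops by arm. The wider set does not correct that selection, so it should at least be visible.

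The cost is a few sentences: no new data, no new model and no change to any clinical rule. The downside is that subjects with protocol deviations enter the wider estimate and could dilute a difference, which is why the per-protocol result stays beside it.
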